Percent change in cortical gray matter volume from Week 24			X
Percent change in white matter volume from Baseline		X	X
Percent change in white matter volume from Week 24			X
Annualized Percentage Change in T1 lesion volume from Baseline to OLE end during the Extended Controlled Treatment and OLE Period		X	X
Annualized Percentage Change in T2 lesion volume from Baseline to OLE end during the Extended Controlled Treatment and OLE Period		X	X
Annualized Percentage Change in Total Brain Volume from Baseline to OLE end during the Extended Controlled Treatment and OLE Period		X	X
Annualized Percentage Change in Cortical Grey Matter Volume from Baseline to OLE end during the Extended Controlled Treatment and OLE Period		X	X
Annualized Percentage Change in White Matter Volume from Baseline to OLE end during the Extended Controlled Treatment and OLE Period		X	X
Descriptive statistics: SF-36, MFIS, NfL			X
Safety Summary: Additional safety data collected during ECP and OLE	X	X	X

9-HPT = 9-hole peg test; ECP = extended controlled treatment period; EDSS = Expanded Disability Status Scale; ITT = intent-to-treat; MFIS = Modified Fatigue Impact Scale; MMRM = Mixed-Effect Model Repeated Measures; MRI = magnetic resonance imaging; MSFCS = Multiple Sclerosis Functional Composite Scale; NfL = Neurofilament Light chain; OLE = open-label extension; T25-FW = timed 25-foot walk.

All analyses performed for the primary CSR are included in this statistical analyses plan. In general, the analyses performed on the extension periods follow the same analyses rules as for the primary CSR. Exceptions have been added in the respective sections.

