4.5.2.3 Change in Total Volume of T2 Lesions on MRI Scans of the Brain from Baseline to Week 120

For the assessment of differences in the percent change in total volume of T2 lesions from baseline up to Week 120, ranked ANCOVA and MMRM analyses will be undertaken using the same approach as described above in Section 4.5.2.2, except that the baseline covariate for the MMRM will be baseline log-transformed T2 lesion volume, geographical region (U.S. vs. ROW), and age (≤ 45 vs. >45 years).

T2 lesion volumes below the lower limit of quantification of 0.009 cm^3 (3 voxels) will be set to this limit.

Extension Periods

This analysis will be extended to include data collected during the OLE period. Ratio relative to baseline until the last mature visit during the combined ECP+OLE period and ratio relative to OLE baseline until the last mature visit during the OLE period will be analyzed. Note that no additional MRI assessments were performed between 120 weeks and OLE start, hence analysis for the ECP period is the same as that for the DB period.

4.5.2.4 Percent Change on MRI from Week 24 to Week 120 in Total Brain Volume

For the assessment of differences in the mean percentage change in brain volume on MRI scans from Week 24 to Week 120, an MMRM analysis will be undertaken using the same approach as described above in Section 4.5.2.2, except:

- The response variable will be the percentage change from Week 24 to subsequent visits (Weeks 48, and 120). Baseline brain volume data will not be a feature in this analysis.
- Covariates will be brain volume at Week 24, geographical region (U.S. vs. ROW), and age (≤ 45 vs. >45 years).

The choice of Week 24 as “baseline” in this analysis, rather than the baseline visit, is a widely accepted approach to establish a stable baseline and avoid the physiological effect of pseudo-atrophy.

Extension Periods

This analysis will be extended to include data collected during the OLE period. Percentage change from Week 24, baseline and OLE baseline until the last mature visit will be analyzed.

4.5.2.5 Change from Baseline in Quality of Life as Measured by the SF36 (Physical Component)

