Time to onset of confirmed EDSS ≥ 7 will be analyzed with EDSS ≥ 7 (requiring wheelchair) to be defined as a disability progression event that is sustained for at least 24 or 48 weeks. The analysis will be conducted as described for the primary analysis.

The analyses will be performed for ECP and the combined DB+OLE periods, with the same baseline as for the analysis during DB. Analysis containing only data from OLE will be performed considering the OLE baseline.

- Annualized Percentage Change in MRI assessments from Baseline during the combined ECP and OLE Periods

Due to the event driven study design and no additional MRI assessments were performed between 120 weeks and OLE start, the time gap between 120 weeks and OLE start varies from patient to patient. Hence, an annualized change in all MRI assessments, including the total brain volume, white matter volume, cortical gray matter volume, T1 lesion volume and T2 lesion volume is analyzed for the combined ECP and OLE periods, which takes into account the variable time difference between visits for each patient.

At each scheduled visit during the ECP and OLE periods, calculate the annualized change from the previous visit as follows:

$$CHG = \frac{\frac{AVAL - lag(AVAL)}{lag(AVAL)} \times 100}{(ADT - lag(ADT))/365.25}$$

where AVAL corresponds to the MRI value at the current visit, and ADT corresponds to the date of the current visit.

For T1 and T2 lesion volume, the log transformation is applied, and 0 values are imputed to 0.009

$$LOGCHG = \frac{\log(AVAL) - \log(lag(AVAL))}{(ADT - lag(ADT))/365.25}$$

The OLE MRI assessments are backdated as follows:

- Create an SoA from Week 120 with a visit every 48 weeks, e.g., Week 168, Week 216, etc
- All OLE visits prior to Week 168 will be assigned to Week 168 ≥ New visit label
- For all remaining OLE visits, they will be assigned to the nearest Week xxx with a time window of ±24 weeks ≥ New visit label
- Use the new visit labels (no OLE Week yy visit label) for the analysis
- If multiple OLE visits are windowed to the same Week xxx visit, then the latest chronological visit will be used for the analyses

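### The annualized MRI change is titled as a change from baseline but computed from the previous visit, and its zero rule, read literally, can score a vanishing one- or two-voxel lesion volume as growth.

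*SAP*

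**What the plan says.** SAP Section 4.2 lists five annualized MRI endpoints (T1 lesion, T2 lesion, total brain, cortical grey matter and white matter volume), all titled in the same form, for example "Annualized Percentage Change in Total Brain Volume from Baseline to OLE end during the Extended Controlled Treatment and OLE Period". They are marked for both the OLE and the combined-extension columns. In Section 4.5.3 the heading of the method is "Annualized Percentage Change in MRI assessments from Baseline during the combined ECP and OLE Periods". The instruction under it is "At each scheduled visit during the ECP and OLE periods, calculate the annualized change from the previous visit", and both formulas use the lagged value and the lagged date:

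- brain volumes: CHG = 100 × (AVAL − lag AVAL)/lag AVAL, divided by (ADT − lag ADT)/365.25;
- lesion volumes: LOGCHG = [log AVAL − log(lag AVAL)], divided by the same time in years.

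On small lesion volumes Section 4.5.3 says: "For T1 and T2 lesion volume, the log transformation is applied, and 0 values are imputed to 0.009". It gives no unit. Section 4.5.2.3, for the secondary T2 endpoint, has a wider rule: "T2 lesion volumes below the lower limit of quantification of 0.009" cm³, given there as 3 voxels, are set to that limit.

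Section 4.2 adds that the extension analyses generally follow the rules of the primary report, and that exceptions are written into the individual sections.

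**The concern.** There are two separate defects.

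**Title against formula.** A table headed as the annualized change from baseline to the end of the extension should hold one rate per patient over that span. The formula yields a series of interval rates, one per visit. The SAP names no summary or model that combines them, so two programmers could fill the same table with different quantities. For lesion volumes the statistic is also a log change per year, while the title promises a percentage.

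**Two rules at the low end.** Replacing zeros, and only zeros, by the quantification limit puts a coded zero above true values of one or two voxels. On a log scale that reverses their order, so the sign of a change can be wrong. A common floor does not have this problem.

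At stake are the long-term atrophy and lesion-volume rates planned for the extension. No primary or secondary analysis is involved.

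**Working it through.** The SAP states no result for this endpoint, so there is no figure to reproduce. The check applies its formulas to small volumes and to example series.

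**Inputs from the documents**
- Limit 0.009 cm³ = 3 voxels (SAP 4.5.2.3), so one voxel is 0.009/3 = 0.003 cm³ and two voxels are 0.006 cm³.
- MRI at baseline and Weeks 24, 48 and 120 (protocol 5.11.2), then a 48-week grid: Week 168, 216 and so on (SAP 4.5.3).
- Time in years: 24 weeks = 168/365.25 = 0.460; 48 weeks = 336/365.25 = 0.920; 72 weeks = 504/365.25 = 1.380.

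**Step 1. The two low-volume rules, 48-week interval**

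| Change (cm³) | Zero rule alone: log change | Per year | With the 4.5.2.3 floor |
|---|---|---|---|
| 0.003 to 0 | ln(0.009/0.003) = +1.099 | +1.19 | 0 |
| 0.006 to 0 | ln(0.009/0.006) = +0.405 | +0.44 | 0 |
| 0 to 0.003 | ln(0.003/0.009) = −1.099 | −1.19 | 0 |
| 0.009 to 0 | ln(0.009/0.009) = 0 | 0 | 0 |
| 0.009 to 0.003 | ln(0.003/0.009) = −1.099 | −1.19 | 0 |
| 0.012 to 0 | ln(0.009/0.012) = −0.288 | −0.31 | −0.31 per year |

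Under the zero rule alone, loss of one voxel counts as growth and a new voxel counts as shrinkage. A fall from 0.009 to nothing also scores as a smaller loss than a fall from 0.009 to one voxel. Over intervals of 24 to 72 weeks the first row ranges from 1.099/0.460 = +2.39 to 1.099/1.380 = +0.80 per year, and the second from +0.88 to +0.29. When the earlier volume is 0.009 or more, a vanishing volume is never scored as growth under either rule.

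**Step 2. Which rule applies**
- *Floor carries over.* Section 4.2 takes the primary-report rules into the extension. Every T2 value below the limit is then already 0.009, the zero rule does nothing, and no false growth arises.
- *Zero rule replaces the floor.* Section 4.2 also says that exceptions are written into the sections, and 4.5.3 states its own rule. Step 1 then applies as shown.

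For T1 the first reading is weaker. The floor is written for T2 only. It reaches T1 through the remark in 4.5.3 that non-enhancing T1 volume is analysed similarly to T2, and that remark concerns the non-annualized endpoint.

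**Step 3. Interval rates against a baseline-to-end rate**
Both series are assumed for illustration, at Weeks 0, 24, 48, 120, 168 and 216. The total time is 1512/365.25 = 4.14 years.

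- T2 volume 10, 11, 11.2, 11.5, 11.6, 11.7 cm³. The interval rates are 0.207, 0.039, 0.019, 0.009 and 0.009 log per year. Their unweighted mean is 0.057 and the last is 0.009. Baseline to end is ln(11.7/10)/4.14 = 0.038.
- Brain volume 1500, 1488, 1484, 1472, 1464, 1456. The unweighted mean of the interval rates is −0.82% per year and the last is −0.59%. Baseline to end is 100 × (−44/1500)/4.14 = −0.71% per year.

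For the log rates only a time-weighted mean returns the baseline-to-end value, and the SAP specifies no mean at all. The size of the gap depends on the assumed series. That the quantities differ does not.

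**The case against.** The strongest reply is that visit-to-visit rates were intended and only the titles are loose. Section 4.5.3 explains that no MRI was done between Week 120 and the start of the extension, that this gap varies between patients, and that annualizing allows for it. Baseline-referenced changes in all five volumes are already planned for the combined period, so the interval rate adds to them. It also has an advantage: Section 4.5.2.4 uses Week 24 as the reference for brain volume to avoid pseudo-atrophy, and interval rates confine early loss to its own interval. This stands. It is a reason to keep the visit-to-visit analysis and correct its title, not to replace the analysis with a baseline rate or a slope model.

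On the low-volume rule, the benign reading in Step 2 is reasonable, and the reply is right that no false growth then occurs. It does not close the point, because the exceptions clause supports the other reading equally well.

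On scale, Section 4.5.2.2 specifies back-transformed estimates and 4.5.2.3 adopts that approach for T2, so a back-transformation may be inherited. What remains is that 4.5.3 defines a log rate under a percentage title without saying so.

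A reader might also infer that these rates are much noisier than they need be. The documents do not support that. A comparison with last-minus-baseline requires an averaging of interval rates that the SAP never specifies. On an equally spaced grid the unweighted mean of the log rates is the baseline-to-end rate, because the intermediate terms cancel. Nor should a withdrawal scan soon after an annual scan normally be annualized over a few weeks: extension scans are windowed to the 48-week grid (±24 weeks) and only the latest in each window is kept.

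**Conclusion.** Two defects hold. The endpoint is titled as a change from baseline in both SAP sections, but its only formula gives the change from the previous visit, with no step to a baseline-to-end value. And the low-volume rule in 4.5.3 differs from the floor in 4.5.2.3 for every volume strictly between 0 and 0.009 cm³.

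If 4.5.3 is applied literally as an exception, one- and two-voxel volumes that vanish score +1.10 and +0.41 log, and new ones score −1.10 and −0.41. If the floor carries over, all of these are 0. So a vanishing volume *can* be scored as growth; the documents do not support saying that it *will* be. Nor do they support reading these log changes as an effect on the reported means, because they do not say how many patients have volumes below the limit.

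The sign problem comes from the zero rule alone, not from the mismatch of title and formula. Primary and secondary endpoints are untouched. This is a small correction to an exploratory endpoint, worth making because the rule as written allows a wrong sign.

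**What to change.** 1. In SAP 4.5.3, set all T1 and T2 lesion volumes below 0.009 cm³ to 0.009 cm³ before taking logs, as 4.5.2.3 does for T2. State the unit, and say explicitly that this covers T1.
2. In Sections 4.2 and 4.5.3, rename the five endpoints as the annualized visit-to-visit change. If a baseline-to-end rate is really wanted, define it as the total log or percent change divided by the total time from baseline.
3. Report lesion-volume rates as 100 × (exp(LOGCHG) − 1) percent per year, or call them log rates.

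The cost is a few lines of SAP wording and one derivation step in an exploratory dataset. No new data are needed and no other endpoint changes.

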4.5.4 Sensitivity Analyses

The following sensitivity analyses of the primary endpoint will be conducted according to the analysis described in Section 4.5.1:

1. The primary analysis will be repeated using the per-protocol population as the analysis population. The below sensitivity analyses will be done with the ITT population.
2. A sensitivity analysis using multiple imputations will be performed for the ITT population to explore the potential influence of informative censoring on the results of the primary efficacy analyses. Censoring for a reason that is not independent of that patient's prognosis is called "informative censoring." The influence of

informative censoring needs to be explored, because for time-to-event endpoints, the ITT principle requires that essentially all randomly assigned patients be observed up to the endpoint or up to the end of the study. When a patient's follow-up is censored X number of months after random assignment, then, in the computation of the Kaplan-Meier estimates, log-rank or Cox regressions, that patient's outcome after X number of months is assumed to have the same outcome as the other patients in their treatment group who also are free of the outcome at X number of months and who remain under follow-up beyond X number of months. Thus, unless the reason for being censored is independent of that patient's prognosis, failure to observe that patient until occurrence of his study endpoints could lead to significant bias as well as increased variability in the evaluation of treatment effects. To censor time to CDP at dropout due to premature withdrawal and lost to follow-up after an initial disability progression is potentially to favor the most toxic or less efficacious treatment and, consequently, should be avoided whenever possible. Thus the purpose of this sensitivity analysis is to determine whether informative censoring has any influence on the primary endpoint.

Multiple imputations will be used to impute the events for patients who had initial disability progression and then discontinued treatment with no confirmatory EDSS assessments. Multiple imputation inference involves three distinct phases:

- The missing data are filled in m times to generate m complete data sets. Instead of filling in a single value for each missing value, multiple imputation replaces each missing value with a set of m plausible values that represent the uncertainty about the right value to impute.
- The m complete data sets are analyzed using standard statistical analyses.
- The results from the m complete data sets are combined to produce inferential results.

Fifty percent of the patients who had initial disability progression and then discontinued the treatment with no confirmatory EDSS assessments will be randomly assigned to have an event at the time of their initial disability progression; the other 50% of these patients will be censored at their last EDSS assessment, under the assumption that 50% of the patients with initial disability progression will later be confirmed at 12 weeks. A total of 1000 (m=1000) imputed datasets will be produced. The primary model described in Section 4.5.1 will be applied to each of the imputed datasets. Each imputed dataset will produce an estimate of the difference between ocrelizumab and placebo. The multiple imputation estimator of the difference between ocrelizumab and placebo is the average of the individual 1000 estimators. The variance of the estimator is the combination of the between- and within-imputation variability ([Carpenter and Kenward 2007](#)).

The 50% confirmation rate for patients with initial disability progression was estimated on the basis of previous studies conducted in patients with PPMS ([Weinshenker et al. 1996](#); Olympus, Study U2786g, data available upon request).

3. A sensitivity analysis, in which the patients who had initial disability progression and then discontinued the treatment with no confirmatory EDSS assessments will be considered to not have CDP, will be performed for the ITT population. This sensitivity analysis assumes that all patients lost to follow up after initial disability progression events will not have reached CDP. Hence, it will give an estimate of the maximal effect of informative censoring on the parameter estimates.
4. The influence of early progression events on treatment effect will also be evaluated by omitting the EDSS assessments performed between randomization and the Week 12 visit (≤ 83 days after randomization) with use of the ITT population.
5. The study originally planned to enroll approximately 630 patients who were to be followed for at least 120 weeks. The study actually enrolled 732 patients (last patient enrolled on 27 December 2012). To explore the effect of the higher enrollment number, the analysis of the primary efficacy endpoint will be performed using the first 630 patients on the basis of their randomization dates (ITT population) at the time of the primary analysis.
6. The primary analysis described above will be adjusted with additional strata for the baseline presence of gadolinium-enhancing T1 lesions (present or absent) and baseline EDSS (≤ 5.5 vs. > 5.5).
7. PPMS is characterized by a progressive course from disease onset typically without superimposed discrete clinical attacks or relapses (Ebers 2004). The primary analysis on CDP for ≥ 12 weeks, described above will be performed excluding patients who have any clinical relapses during the study. Clinical relapses include protocol-defined relapses.
8. For the time to onset of CDP for ≥ 24 weeks, the influence of early progression events on treatment effect will also be evaluated by omitting the EDSS assessments performed between randomization and the Week 12 visit (≤ 83 days after randomization) with use of the ITT population.
9. For the time to onset of CDP for ≥ 24 weeks, the analysis will be performed excluding patients who have any clinical relapses during the blinded treatment period.

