4.3 ANALYSIS OF STUDY CONDUCT

The following analyses will be conducted to evaluate the study conduct:

- Summary of protocol deviations
- Summaries of ITT, per protocol defined, and safety populations, including numbers of patients in each population, and reasons for exclusion from the per-protocol population

- Summary of subject disposition, including the number of treatment doses received, and the number of patients entering into SFU
- Summary and Kaplan-Meier plots of:
 - Time to discontinuation of study treatment during the blinded treatment period. (All other patients will be censored at their last assessment during the blinded treatment period)
 - Time to discontinuation from the study (All other patients will be censored at their last assessment during the study)

Extension Periods

The summary of subject disposition will be updated using additional data from the ECP and OLE periods, including the number of patients entering into and withdrawing from OLE and into/from OLE SFU.

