An independent examining investigator at each study site will assess EDSS for all patients at the site at screening, baseline, every 12 weeks (regularly scheduled visit) during the blinded treatment period of the study, during the SFU period, at any unscheduled visits, and at withdrawal from treatment and end of study visits. Additional EDSS assessments for individual patients may be requested between visits (i.e., during an MS relapse).

The examining investigator is not the physician responsible for the patient care (the treating investigator).

The EDSS is based on a standard neurological examination; the seven categories of the EDSS representing FS (pyramidal, cerebellar, brainstem, sensory, bowel and bladder, visual, and cerebral [or mental], plus "other") are rated and scored (collectively, FSs), in addition to an ambulation score (0–12). Each domain of the FS is an ordinal clinical rating scale from 0 to 5 or 6. These ratings are then used in conjunction with observations and information regarding ambulation and the use of assistive devices (which will also be scored) to determine the EDSS score. The EDSS is a disability scale that ranges in 0.5point steps from 0 (normal) to 10.0 (death).

Analysis Methods

The ITT population analysis will be presented.

Patients who did not have initial disability progression at the time of primary database lock, time of early discontinuation, or loss to follow-up will be censored at the date of their last EDSS assessment that occurred during the treatment period.

There are various options to obtain EDSS assessments (confirmatory and non-confirmatory) and to record how the discontinuation from treatment and study can influence the confirmation of the disability progression. The following rules apply for all patients with initial disability progression:

- Initial disability progression must occur when the patient is still on treatment.
- All non-confirmatory EDSS assessments (if any) after initial disability progression and up to and including the confirmatory EDSS assessment should also fulfill the requirements of the progression as defined above. Otherwise an initial disability progression event cannot be confirmed.

Patients who experience initial disability progression will be treated as described in [Table 2](#)).

Table 2 Censoring Algorithm of Patients after Initial Disability Progression

Availability of EDSS Assessment for Patient with Initial Disability Progression	Recorded Disability Progression Status

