Scenario A: Confirmatory EDSS assessment on treatment or after withdrawal from treatment	Confirmed disability progression
Scenario B: No confirmatory EDSS assessment; patient on treatment at the time of primary database lock	Censored at last EDSS assessment
Scenario C: Discontinues from treatment and is lost to follow-up; i.e., no available EDSS assessment at ≥ 84 days after initial disability progression	Confirmed disability progression

EDSS=Expanded Disability Status Scale.

The time to onset of CDP for the ocrelizumab arm and the placebo arm will be compared using a two-sided log-rank test stratified by geographic region (U.S. vs. ROW) and age (≤ 45 vs. > 45 years). The proportion of patients with CDP at predefined timepoints (i.e., 48 weeks, 96 weeks, etc.) will be estimated using Kaplan-Meier methodology. The overall hazard ratio will be estimated using a stratified Cox regression model with the same stratification factors used in the aforementioned stratified log-rank test.

Sample SAS code can be found below (SAS code is regarded as “draft” until fully validated at the analysis stage):

```
* Log-rank test;
proc lifetest data=CDP12;
  time CDP12TIME*CNSR(1);
  strata REGION AGE45 / group=ARMCD;
  ods output HomTests =_logrank;
run;

* Cox regression model;
proc phreg data=CDP12;
  class ARMCD / descending;
  model CDP12TIME*CNSR(1) = ARMCD / rl;
  strata REGION AGE45;
  ods output ParameterEstimates=est;
run;
```

Extension periods

This analysis will be repeated to include the EDSS assessments performed during the ECP and OLE periods for ECP and the combined double blind (DB)+OLE periods, with the same baseline as for the analysis during DB. Analysis containing only data from OLE will be performed considering the OLE baseline.

Patients discontinuing from either treatment periods (ECP or OLE) after initial disability progression and without confirmatory EDSS assessment will be imputed.

For the OLE period, initial disability progression has to occur while the patient is on OLE treatment. Confirmation of progression could occur at scheduled OLE or SFU visits after the OLE.

The same principle applies to all time to CDP endpoints below.

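### SAP 4.5.4 item 3 is described as the maximal effect of informative censoring, but it applies one confirmation rate to both arms and so does not bound that effect

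*SAP*

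**What the plan says.** SAP 4.5.1, Table 2, sets the primary rule. A patient with an initial progression who stops treatment and has no EDSS 84 days or more later counts as a confirmed event (Scenario C). Off-treatment assessments can still confirm (Scenario A: "Confirmatory EDSS assessment on treatment or after withdrawal from treatment"). A patient without an initial progression who stops early "will be censored at the date of their last EDSS assessment that occurred during the treatment period".

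SAP 4.5.4 then lists two analyses of missing confirmation.

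- Item 2 uses multiple imputation to "impute the events for patients who had initial disability progression and then discontinued treatment with no confirmatory EDSS assessments", "under the assumption that 50% of the patients with initial disability progression will later be confirmed at 12 weeks". No separate rate is given for each arm. Its rationale warns that "failure to observe that patient until occurrence of his study endpoints could lead to significant bias" and says that "the purpose of this sensitivity analysis is to determine whether informative censoring has any influence on the primary endpoint".
- Item 3 counts none of these patients as confirmed, in either arm, and concludes: "Hence, it will give an estimate of the maximal effect of informative censoring on the parameter estimates".

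The list is headed as covering the primary endpoint. For 24-week progression it contains only item 8 (early EDSS values omitted) and item 9 (relapsing patients excluded), although SAP 4.5.2.1 analyses that endpoint as the primary one. SAP 4.3 adds Kaplan-Meier summaries, including "Time to discontinuation of study treatment during the blinded treatment period". SAP 4.8 adds no further missing-data method.

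**The concern.** The effect of informative censoring is the gap between what is estimated and what would have been seen with full follow-up. Item 3 against the primary analysis shows that gap for one pair of assumptions: everybody confirms, or nobody does, with the arms treated alike. Informative censoring is most harmful when the arms differ, and no planned rule lets them differ.

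Three gaps follow. Item 3 is not an outer limit even for the patients it re-scores. Withdrawals without an initial progression are never re-scored, although the stated purpose of item 2 is broader; the summaries in SAP 4.3 describe discontinuation but leave the endpoint as it is. And 24-week progression, the first secondary endpoint in the testing order, uses the same counting rule with a longer window and has no matching sensitivity analysis.

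At stake is what the robustness analysis is said to prove: a reader could take item 3 as the furthest that missing confirmation could move the hazard ratio.

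**Working it through.** **1. The plan's own figures.** The disputed sentence states no number, so the check starts from SAP 2.2. Two-year progression of 43% and 30% gives hazards -ln(0.57)/2 = 0.281 and -ln(0.70)/2 = 0.178 per year, ratio 0.635 as stated. Dropout of 20% over 2 years gives -ln(0.8)/2 = 0.1116 per year. With 2:1 allocation, 1-year accrual and 3.5 years in total, expected events are 253.5 for 630 patients (stated 253) and 294.5 for 732 (stated 295). The design figures reproduce and are not affected by this point.

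**2. The logic, which needs no counts.** Let E_p and E_o be events confirmed in the ordinary way (placebo, ocrelizumab), and n_p and n_o the unconfirmed discontinuers. Re-scoring a few patients barely changes person-time, so the hazard ratio moves almost in proportion to event counts. Relative to the primary analysis:

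- 0% placebo, 100% ocrelizumab: U = (E_p + n_p)/E_p, above 1
- 100% placebo, 0% ocrelizumab: D = E_o/(E_o + n_o), below 1
- item 3 (0% in both): U × D

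Whenever both arms have at least one such patient, U × D lies strictly between D and U. Whichever way item 3 moves the hazard ratio, one arm-specific rule moves it further the same way. If n_p/E_p = n_o/E_o, then U × D = 1 and item 3 shows no movement at all.

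**3. An illustrative count (assumed).** The share of patients dropping out within 84 days is 1 - exp(-0.1116 × 84/365.25) = 2.5%. With 253 events and the SAP's 50% confirmation rate there are 253/0.5 = 506 initial progressions, and 2.5% of these is about 13. This treats dropout as unrelated to progression, so it is only an order of magnitude. Split in proportion to events, the 13 become about 5 placebo and 8 ocrelizumab; other splits are shown because nothing in the documents fixes this one.

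**4. Results.** The simulation uses exponential hazards scaled by 0.80, accrual over 1.5 years (assumed) and 244:488 patients, giving E_p = 104 and E_o = 147. The Cox model is unstratified.

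| Split (placebo/ocrelizumab) | Item 3 ÷ primary (U × D) | U | D | Simulated HR: primary, item 3, 0%/100% extreme |
|---|---|---|---|---|
| 5/8 | 0.994 | 1.048 | 0.948 | 0.637, 0.633, 0.668 |
| 8/5 | 1.042 | 1.077 | 0.967 | 0.611, 0.637, 0.659 |
| 10/3 | 1.074 | 1.096 | 0.980 | 0.589, 0.634, 0.647 |
| 2/11 | 0.948 | 1.019 | 0.930 | 0.675, 0.639, not simulated |

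Worked line for 5/8: U = 109/104 = 1.048, D = 147/155 = 0.948, product 0.994. The 5/8 primary value is 0.633/0.994 = 0.637. For 2/11 the extreme relative to item 3 is 158/147 = 1.075, so about 0.639 × 1.075 = 0.687. Milder arm-specific rates at 5/8 (25% placebo, 75% ocrelizumab, and the reverse) give ratios to primary of 1.023 and 0.972 in simulation.

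**5. 24-week progression.** A 168-day window gives 1 - exp(-0.1116 × 168/365.25) = 5.0%, or about 25 patients (10/15). With event numbers assumed as for 12 weeks, item 3 gives 0.635 and the 0%/100% extreme 0.703. The SAP's 161-day threshold gives a slightly smaller share (4.8%).

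**6. Larger counts.** Suppose 20% of placebo events and 10% of ocrelizumab events were unconfirmed discontinuers (about 24 and 17 patients among 295 events). Simulated hazard ratios are then 0.637 primary, 0.719 item 3 and 0.798 at the extreme, with p at the mean test statistic of about 0.0001, 0.011 and 0.075.

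**The case against.** The best defence is contextual. The rationale in item 2 dwells on loss after an initial progression. The primary analysis censors none of these patients and item 3 censors all of them, and item 3 states its assumption openly just before the disputed sentence. Read as the full switch from counting to censoring one defined group, the word maximal can be defended. But the sentence speaks of informative censoring and of the parameter estimates, and for those a limit that holds only when both arms share one rate is not a limit.

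Other parts of the defence stand:

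- Item 3 is informative. A reader might infer that the planned analyses would show stability whatever the data. That holds only if the patients split roughly as events do. At 8/5, 10/3 and 2/11, item 3 moves the hazard ratio by about +4%, +8% and -5%, so it does detect unequal numbers of imputed events.
- The number of such patients may be small. EDSS continues every 12 weeks in safety follow-up and can confirm off treatment, and assessors are blinded, which makes 0% against 100% an extreme rather than a likely case.
- Re-scoring withdrawals without an initial progression partly answers a different question. SAP 4.5.1 requires the initial progression to occur on treatment, so following these patients to the administrative end targets progression that the endpoint excludes.
- SAP 4.5.4 is headed for the primary endpoint, so the 24-week omission is a gap in coverage and not a contradiction.

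**Conclusion.** The sentence claims a property that item 3 does not have. This follows from the counting rules alone and holds for any counts with at least one such patient in each arm. The three gaps (one common rate, withdrawals without initial progression left as they are, 24-week progression not covered) match the text.

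The size is unknown, because the documents give no counts of these patients by arm. With 13 patients, the 0%/100% extreme exceeds item 3 by between 2% (10/3: 0.647 against 0.634) and 7.5% (2/11). These figures rest on the assumed count, the assumed splits, exponential hazards and an unstratified model.

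A reader might go further and infer either that significance is safe or that the primary result is in doubt. The documents support neither: the extreme leaves clear significance at small counts and gives p of about 0.075 at the larger assumed counts in step 6. Protocol Appendix 8 reports that the primary endpoint was met, and nothing here challenges that. Severity: minor.

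**What to change.** Leave the primary analysis and Table 2 as they are.

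1. Replace the closing sentence of item 3 with: *This analysis shows the result if no such patient in either arm would have confirmed; it does not address confirmation rates that differ by arm or censoring at withdrawal without initial progression.*
2. Report the number of these patients by arm, with a tipping-point grid that varies the confirmation rate from 0 to 100% separately in each arm.
3. Run items 2 and 3 and the grid for 24-week progression.

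Label 2 and 3 supplementary and specified after unblinding. A delta-adjusted or reference-based analysis of withdrawals without initial progression is optional; if run, it should state that it targets progression after treatment stops, which the endpoint definition excludes.

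The cost is one sentence of SAP text and a few runs on data already collected. The drawback is that the additions are post hoc for an analysis already reported, and robustness may look less favourable than the present wording suggests. The counts by arm alone would show whether the issue is trivial.
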